26.2 Appendix 2 Instructions for Use

AddBIO

Instructions for use Zolidd One ExHex – SE
Date: Revision 4 2017-04-28

AddBIO AB, [name]
[name]

Produktbeskrivning

Zolidd One ExHex är ett dentalimplantat som tillhandahålls i två olika utföranden, dels obelagda och dels belagda med den bioaktiva beläggningen Zolidd.

De belagda implantaten har belagts med ytan Zolidd för att påskynda inläkningen av implantatet, speciellt i områden med sämre benkvalitet. Zolidd består av ett nanolager humant blodprotein samt bisfosfonat.

Implantatet är ett skruvformat titanimplantat (titan grad 4) av storlek Ø4.0x10mm med en marginalanpassning för R (reguljär 3,75 och 4mm) profil så kallad "external hex design".

Implantatet är en generisk variation på Nobel Biocares originalimplantat designat av MkIV och därav kompatibelt med kirurgiska och protetiska komponenter för MkIV.

Kompatibilitet

Implantatet är kompatibelt med instrument, borrh och protetiska komponenter från Nobel Biocare, enligt *ad modum* Bränemark.

Indikationer

Partiellt tandlöshet

Varningar, försiktighetsåtgärder och kontraindikationer

Samma generella försiktighetsåtgärder gäller som vid alla dentala implantatoperationer.

Endast käkkirurger eller tandläkare med lång erfarenhet av att installera dentala implantat i enlighet med *ad modum* Bränemark skall använda AddBIOs implantat.

Kända riskfaktorer inkluderar otillräcklig benvolym, infektion, otillräcklig mjukvävnad, okontrollerad diabetes, rökning, bruxism, ogynnsamma käkförhållanden, oro-facial strålbehandling, steroidbehandling, systemisk behandling med bisfosfonat samt cellgiftsbehandling.

Patienter med allergier mot titan, zoledronat (bisfosfonat) eller andra bisfosfonater, eller fibrinogen-koncentrat bör inte behandlas med detta implantat.

Fibrinogen framställs från blod som kommer från bloddonatorer. Vid tillverkningen vidtas speciella åtgärder för att förhindra att infektioner överförs till patienter. Detta inkluderar ett noggrant urval av blod- och plasmagivare för att säkerställa att personer med risk för att vara smittbärare utesluts, samt test av enskilda donationer och plasmapooler för tecken på virus/infektion. Tillverkaren av läkemedlet inkluderar dessutom steg i hanteringen som kan inaktivera eller avskilja eventuella virus. Trots detta kan risken för överföring av infektion inte helt uteslutas när läkemedel framställda ur humant blod eller plasma ges. Detta gäller även okända eller nya virus och andra typer av infektioner.

Implantatet är säkert vid MR undersökning men kan orsaka bildartefakter.

Sterilitet

Implantaten tillhandahålls sterila. Om antingen implantatet eller förpackningen verkar skadade, om utgångsdatum passerat eller om steriliteten av något annat skäl ifrågasätts, ska implantatet inte användas. Produkten får inte återanvändas eller om-steriliseras då detta kan påverka ytbeläggningen negativt.

Tillvägagångssätt

1. Patienten förbereds för implantatoperation med en utvidgad medicinsk och oral undersökning.
2. Benkvalitet och viktiga anatomiska strukturer fastställs med hjälp av lämpliga röntgenologiska utvärderingar i de tandlösa posteriora områdena.
3. Vid operationstillfället skall området bedövas, vanligtvis med lokal bedövning.
4. Tandköttet klaffas upp enligt implantatkirurgisk standardmodell.
5. De fastställda implantatsätena (kan vara enstaka eller multipla) markeras med ett rundborr eller direkt med spiralborr. Därefter borras de med spiralborr med stigande storlek från $\varnothing 2.0 \times 10\text{mm}$ till "Twist step drill" $\varnothing 2.4/2.8 \times 10\text{mm}$ och $\varnothing 2.8/3.2 \times 10\text{mm}$ för de mjukaste kvaliteterna. När benet ger mer motstånd som i medium till hårt ben kan även ett $\varnothing 3.2/3.6 \times 10\text{mm}$ borr användas. Följ instruktionerna enligt IFU för MkIV. Max borrhastighet är 2000 varv/minut med adekvat NaCl spolning.
6. Implantatsätet förgängas ej, och implantatet installeras med maxhastighet 25 varv/minut och med max 45 Ncm. När implantatet nått sitt rätta läge i sätet skall kirurgen manuellt känna att det är stabilt. ISQ skall användas för att mäta stabiliteten.
7. En läkdistans sätts på implantatet och operationssåret sys ihop.
8. Eventuella stygn tas bort efter ca 2 veckor

9. Implantationen sker enligt så kallad 1-stegsförfarande. Det vill säga att en läkdistans placeras på implantatet vid operationstillfället. Direkt belastning av implantatet skall undvikas under inläkningsperioden på 3 månader.

10. Inför avtryckstagning avlägsnas först läkdistansen. Sedan skall ISQ mätas för att fastställa att stabiliteten är acceptabel. Har stabiliteten minskat i stället för ökat jämfört med det tidigare ISQ värdet bör förlängd inläkningstid övervägas. Är implantatet helt mobilt kan ett nytt implantat sättas i sätet. Avtryck för protetik sker efter att läkdistansen avlägsnats och enligt gängse förfarande med avtryckstagning med öppen sked först. Läkdistansen sätts tillbaka på plats igen till dess att det protetiska arbetet är klart och skall sättas på plats.

11. Implantatavtrycket tillsammans med ett avtryck på motstående käke och en bitning skickas till tandtekniskt lab. för framställning av lämplig protetisk konstruktion.

12. När protetiken är klar tas läkdistansen av och protetiken ansluts. Den protetiska (bro)konstruktionen skall passa passivt utan att någon kraft används när den skruvretineras på plats enligt *ad modum* Bränemark.

13. Post-protetisk uppföljning sker enligt standardförfarande *ad modum* Bränemark med årlig oral undersökning och röntgen efter år 1 och 2 därefter med längre intervall.

14. Patienten informeras om hur man håller rent kring sina ersättningar och om att utan dröjsmål kontakta behandlande tandläkare vid eventuella besvär.

**A randomized, double blind, parallel study to evaluate the performance and safety of the Zolidd One ExHex dental implant in subjects with partial edentulism**

Protocol No:

ADD-001

Version:

1.0

Page 4 of 18

## LIST OF ABBREVIATIONS

Abbreviation	Definition
AE	Adverse Event
ADE	Adverse Device Effect
ANCOVA	Analysis of Covariance
ATC	Anatomical Therapeutic Chemical Classification
CI	Confidence Interval
DD	Device Deficiency
DMFT	Decayed Missed Filled Teeth
GEE	Generalized estimating equation
ISQ	Implant Stability Quotient
ITT	Intention-to-Treat
LOCF	Last Observation Carried Forward
MedDRA	Medical dictionary Drug Regulatory Affairs
PP	Per Protocol
PT	Preferred term
SADE	Serious Adverse Device Effect
SAE	Serious Adverse Event
SD	Standard Deviation
SOC	System Organ Class

STATISTISKA KONSULTGRUPPEN		Statistical Analysis Plan	
Protocol: A randomized, double blind, parallel study to evaluate the performance and safety of the Zolidd One ExHex dental implant in subjects with partial edentulism		Protocol No: ADD-001	Version: 1.0 Page 5 of 18

## 1 STUDY DETAILS

### 1.1 Study Objectives

#### Primary Objective

The primary objective is to compare the change in stability from day 1 (implantation) to 12 weeks after surgery of the “index implant” between coated and uncoated implants.

#### Secondary Objectives

##### The secondary objectives Part I:

- To compare absolute ISQ highest values between coated and uncoated “index implants” at week 8 and week 12 after implantation
- To compare safety as assessed by complications post-surgery and any other adverse event up to week 12 between all coated and all uncoated implants
- To compare change in stability from day 1 to week 8 between the coated and the uncoated “index implants”
- To compare change in stability day 1 to week 8 and 12 between all other coated and all other uncoated implants
- To compare absolute ISQ highest value at week 8 and 12 between all other coated and all other uncoated implants
- To compare change in marginal bone height between all coated and all uncoated implants from day 1 to week 8 and 12
- To compare survival rate of implants up to 12 weeks between all coated and all uncoated implants

##### The secondary objectives Part II:

- To compare safety as assessed by complications post-surgery and other adverse events up to month 24 post-implantation visit between all coated and all uncoated implants
- To compare survival rate of implants up to 24 months between all coated and all uncoated implants
- To compare change in marginal bone height from day 1 to month 12 and 24 between all coated and all uncoated implants
- To compare signs of peri-implantitis frequency at 12 and 24 months between all coated and all uncoated implants.

### 1.2 Study Design

This is a randomised, multicentre double-blind, parallel study where subjects will be randomised to receive coated or uncoated dental implant. Subjects will be assessed during the 12 weeks’ post-operative period (Part I) with an extended Post follow-up period up to 24 months after implantation (Part II). There will be two Clean file meetings, two data-base locks, two reports with tables, figures and analyses. One for Part I when all subjects have completed 12 weeks visit and one after all subjects have completed the 24 months follow-up. Marginal bone loss data will be analyzed and locked only once, at the end of the study, and all time-points will be analyzed at that time.

## Part I

Protocol:

**A randomized, double blind, parallel study to evaluate the performance and safety of the Zolidd One ExHex dental implant in subjects with partial edentulism**

[figure not shown]
Protocol No:

ADD-001

[figure not shown]
Version:

1.0

Page 6 of 18

## **Part II (post follow-up)**

### **1.3 Treatment Groups**

The test implant, Zolidd One ExHex, and the control implant One ExHex consist of a generic model of the established Bränemark dental implant. The test implant is coated with Zolidd and the control implant is uncoated. Zolidd is a nano-coating combination of heated fibrinogen and zoledronic acid which adheres to the surface of the thread profiles of the dental implants. This Zolidd coating is aimed to enhance the bone integration properties, by strengthening the bone surrounding the implant. The control implant, One ExHex is blasted and cleaned according to the same protocol as the coated implant. The only difference between the control and the coated implants are the addition of Zolidd. Both of the coating ingredients of the Zolidd coating have a long established history of use as pharmaceuticals.

### **1.4 Sample Size**

The power analysis based on Abtahi et al. 2012: The SD for change in ISQ value from placement to month 6 was 5.3 in the active group and 5.4 in the control group. In order to be able to find a clinical difference of five ISQ highest values in change between placement and 12 weeks between the coated and the uncoated group with Fisher's non-parametric permutation test with 90% power 28 evaluable subjects are needed in each group assuming a SD for change in ISQ in each group of 5.6 and a significance level 0.05. Thirty-one subjects will be randomized to each study group to compensate for 10% drop-out. A total of 62 subjects will be randomized to the two groups.

STATISTISKA KONSULTGRUPPEN		Statistical Analysis Plan	
Protocol: A randomized, double blind, parallel study to evaluate the performance and safety of the Zolidd One ExHex dental implant in subjects with partial edentulism		Protocol No: ADD-001	Version: 1.0 Page 7 of 18

### 3 STUDY VARIABLES

#### 3.1 Baseline Variables

##### 3.1.1 Demographics and Baseline Characteristics

- Age
- Gender
- Childbearing status
- Implant position
- Alcohol status

STATISTISKA KONSULTGRUPPEN		Statistical Analysis Plan	
Protocol: A randomized, double blind, parallel study to evaluate the performance and safety of the Zolidd One ExHex dental implant in subjects with partial edentulism		Protocol No: ADD-001	Version: 1.0

### 3.1.2 *Tobacco status* *Surgical Variables*

Implants position.

### 3.1.3 *Medical History*

Each category will be coded as Past or Current.

### 3.1.4 *Prior and Concomitant Medications and Other Dental Procedures*

At each visit the concomitant medication and procedure will be collected. The medication will be coded with ATC code.

## 3.2 **Efficacy Variables**

ISQ values and measured at Day 1, 8 weeks and 12 weeks from surgery and x-ray with measurement of marginal bone height will be performed Day 1, 8 weeks, 12 weeks, 12 months and 24 months from surgery

### 3.2.1 *Primary Efficacy Variable*

The primary endpoint is change in stability from day 1 to 12 weeks after implantation of the “index implant” comparing coated and uncoated implants. This will be assessed in terms of induced micro motion of the implant using the Osstell device. The ISQ values are recorded from two directions. The directions should be bucco-lingual and mesio-distal, whereof highest value of the two measurements will be used in the analyses.

### 3.2.2 *Secondary Efficacy Variables for Part I*

- Absolute ISQ highest value at day 1, week 8 and week 12 after implantation for “index implant”
- Incidence of post-surgery complications and adverse events up to week 12 post-implantation visit
- Change in ISQ highest value from day 1 to 8 weeks for the “index implant”
- Change in ISQ highest value from day 1 to week 8 and 12 for all other implants
- Absolute ISQ highest value at day 1, week 8 and 12 for all other implants
- Survival rate up to 12 weeks for all implants.

### 3.2.3 *Secondary Efficacy Variables for Part II*

- Post-surgical complications and other adverse events up to month 24 post-implantation visit for all implants
- Survival rate up to 24 months for all implants
- Marginal bone height at day 1, week 8, week 12, month 12 and month 24 for all implants

STATISTISKA KONSULTGRUPPEN		Statistical Analysis Plan	
Protocol: A randomized, double blind, parallel study to evaluate the performance and safety of the Zolidd One ExHex dental implant in subjects with partial edentulism		Protocol No: ADD-001	Version: 1.0 Page 10 of 18

- Change in marginal bone height from day 1 to week 8, week 12, month 12 and month 24 for all implants
- Occurrence of signs associated with peri-implantitis at month 12 and month 24 for all implants

### 3.3 Safety Variables

#### 3.3.1 Adverse Events/Serious Adverse Events/Adverse Device Effects/Serious Adverse Device Effects/ Device Deficiencies

Adverse events (AEs), Serious Adverse Events (SAEs), Adverse Device Effects (ADEs), Serious Adverse Device Effects (SADEs), Device Deficiencies (DDs) are collected at all visits during the study. Treatment emergent events are new events after surgery or old events with wors severity. The events will be coded with MedDRA dictionary.

#### 3.3.2 Implant Status and Soft Tissue Status

Implant status and Soft tissue status are measured at each visit.

Implant status is coded as: OK / Questionable / Loose.

Soft tissue status is coded: Neither red or swollen / Red / Swollen / Red and swollen

#### 3.3.1 Dental Examination

Dental examination will be performed at all visits except visit 3, 2 week visit surgery. Decayed Missed Filled Teeth (DMFT) is not performed at one of the sites and will therefore only be summarized for a subgroup of subjects.

## 4 STATISTICAL METHODOLOGY

### 4.1 General Methodology

The design of the study is a two parallel group design. All main efficacy analyses will be performed on the ITT population. Complementary efficacy analyses will be performed on the PP population.

For comparison between the two groups (coated vs uncoated), when we have only one observation per subject, Fisher's non-parametric permutation test will be used for continuous variables, Fisher's exact test for dichotomous variables, Mantel-Haenszel chi-square test for ordered categorical variables and Chi-square test for unordered categorical variables.

For primary efficacy variables and for other important continuous efficacy variables the mean difference between the two groups with 95% confidence interval (CI) will be given. For dichotomous variables the percentage in each group together with the difference in percentage between the two groups with 95% confidence interval will be calculated with Miettinen and Nurminen's method.

If clinically relevant significant differences are found between the two randomised groups in important baseline predictors a complementary primary efficacy analyses will be performed

STATISTISKA KONSULTGRUPPEN		Statistical Analysis Plan	
Protocol: A randomized, double blind, parallel study to evaluate the performance and safety of the Zolidd One ExHex dental implant in subjects with partial edentulism		Protocol No: ADD-001	Version: 1.0 Page 11 of 18

adjusted for these variables using analysis of covariance (ANCOVA) for continuous outcome variables and with multivariable logistic regression for dichotomous outcome variables.

For comparison between the two groups (coated vs uncoated), when we have more than one observation for all or for some subjects, a mixed model with random effects will be used for continuous outcome variables and a General Estimating Equation (GEE) model is used for dichotomous outcome variables. In both these models the dependence within observation are taken into account correctly. For non-normal continuous variables the mixed model will include an empirical bias correction with robust standard errors.

For comparison over time of index implants within randomized groups Fisher's non-parametric permutation test for paired observations will be used for change in continuous and Sign test for change in ordered categorical variables or change in dichotomous variables. When all implants are analyzed the same methods as specified above, i.e. mixed and GEE models will be applied.

The distribution of the variables will be given as mean, SD, median, minimum and maximum for continuous variables and as number and percentages for categorical variables.

The survival rate of implant (implant loss) will be described with Kaplan-Meier curves with 95% CIs adjusted for within-subject correlation and analyzed with suitable Log-rank test, also adjusted for within-subject correlation, between the two randomised groups.

All tests will be two-tailed and conducted at 0.05 significance level. All analyses will be performed by using SAS® v9.2 (Cary, NC).

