14.3.2 Inclusion criteria

The subject is eligible for inclusion in the study if all of the following criteria are met:

- Male or female subjects aged ≥ 18 years
- Subjects should be willing to take part, able to understand the information given to them, and give written consent
- Subject diagnosed with partial edentulism and who needs at least one dental implant in the posterior upper jaw i.e. premolars to first molar The same subject may also need implants in the posterior mandible (premolar to first molar region)

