18.2 General methodology

The design of the study is a two parallel group design. The main efficacy analyses will be performed on the Intention-to-Treat (ITT) populations between the two groups. Complementary performance analyses will be performed on the Per Protocol (PP) population. See section 18.4 below.

For comparison between the two randomized groups regarding “index implant”, Fisher’s non-parametric permutation test will be used for continuous variables, Mantel-Haenszel chi-square test for ordered categorical variables, and Chi-square test for non-ordered categorical variables and Fisher’s exact test for dichotomous variables.

For primary efficacy variables and for other important continuous efficacy variables the 95% confidence interval for the mean difference between the two groups will be obtained by inversion of Fisher’s non-parametric permutation test by means of simulation.

For comparison between the two randomized groups regarding analysis of all teeth within subjects a mixed model with random effects analysis adjusting for within subject correlation will be used.

If significant clinical relevant differences are found between the two randomised groups in important baseline variables, then complementary efficacy analyses will be performed adjusted for these variables.

For comparison over time within randomized groups Fisher’s non-parametric permutation test for paired observations will be used for change in continuous and Sign test for change in ordered categorical variables or change in dichotomous variables.

The distribution of the variables will be given as mean, SD, median, minimum and maximum for continuous variables and as number and percentages for categorical variables.

Time to loss of implant will be described with Kaplan-Meier curves and analysed with Log-rank test between the two randomised groups.

All significance tests will be two-sided and conducted at the 5% significance level.

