18.3 Statistical hypothesis

Primary Objective – the hypothesis is that there will be improved early stability of the “index implant” observed with the coated than with the uncoated implants, determined with change in ISQ values from day 1 to 12 weeks after insertion.

Secondary Objectives – the hypothesis is that there will be improved early stability of the “index implant” observed with the coated than with the uncoated implants, determined with change in ISQ values from day 1 to 8 weeks after insertion.

Furthermore— the hypothesis is that there will be improved early stability of all implants observed with the coated than with the uncoated implants, determined with change in ISQ values from day 1 to week 8 and 12 after insertion and determined with ISQ values at week 8 and week 12.

The hypothesis is also that there will be less marginal bone loss for coated compared to uncoated implants from implantation to week 8 and 12.

At the post follow-up visits at month 12 and 24 it is anticipated that this difference will be greater in the maxillary teeth as mandibular bone is usually of better quality. At month 12 and 24 post follow-up compare safety, survival rate and change in marginal bone height from implantation between coated and uncoated implants.

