#### 4.6 Surgical Variables

Implants position will be summarized for each treatment group for ITT population.

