#### 4.8.2 Secondary Efficacy Analyses Part I

Secondary efficacy analyses for Part I will be the comparison between the two randomized groups regarding all the secondary efficacy variables given in section 3.2.2 using the statistical methodology given in sections 4.1 above on the ITT-population.

Complementary analyses between the two randomized groups of secondary efficacy variables will be done on the PP-population.

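### The secondary mixed models for non-index implants (ISQ) and all implants (marginal bone height) pool both jaws with no jaw term; precision is lost if jaw predicts the outcome

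*SAP*

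**What the plan says.** Protocol 18.2 prescribes, for analyses of all teeth within subjects, that "a mixed model with random effects analysis adjusting for within subject correlation will be used". SAP 4.1 repeats this for continuous outcomes with more than one observation per subject: "a mixed model with random effects will be used for continuous outcome variables". Neither names a covariate. SAP 4.8.2 analyses the Part I secondary variables "using the statistical methodology given in sections 4.1 above on the ITT-population", and SAP 4.8.3 does the same for Part II.

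The continuous variables concerned are:

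- ISQ for non-index implants (SAP 3.2.2): "Change in ISQ highest value from day 1 to week 8 and 12 for all other implants" and "Absolute ISQ highest value at day 1, week 8 and 12 for all other implants".
- Marginal bone height, level and change, for all implants (SAP 3.2.3).

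On jaw and position, the documents say:

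- The index implant is always maxillary (Protocol 10). Additional implants in the posterior mandible are allowed (Protocol 14.3.2), up to six implants per subject.
- Protocol 18.3 expects the coated-uncoated difference at months 12 and 24 to be "greater in the maxillary teeth as mandibular bone is usually of better quality".
- SAP 4.6: "Implants position will be summarized for each treatment group for ITT population".
- SAP 4.8.4 lists implant position among the candidate predictors in exploratory stepwise models on all implants.
- SAP 4.8.5 limits interaction analyses to the primary variable.
- Adjustment for baseline differences is complementary and triggered by significance. Protocol 18.2 applies it to efficacy analyses generally; SAP 4.1 applies it to the primary analysis only.

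**The concern.** The jaw mix among non-index implants is set by clinical need. The blocked 1:1 randomisation in Protocol 18.9 aims at balance across centres and states no stratification by jaw. With 62 subjects, of whom only some contribute further implants, one arm can by chance hold noticeably more mandibular sites. If mandibular implants have different ISQ or bone height, that imbalance passes into the treatment estimate, and the random intercept does not remove it.

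At stake is the precision of the secondary ISQ and bone-height comparisons, and how readily they can be defended. If the jaw mix turns out unequal and no adjustment was prespecified, an adjusted result will look post hoc and an unadjusted one will invite challenge. Absolute ISQ in non-index implants looks most exposed, because it compares levels and no day 1 value is subtracted.

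**Working it through.** **The plan's own figure.** The documents give no power or precision for the multi-implant models. The only stated figure is for the index implant: difference 5, SD 5.6, 90% power, two-sided 0.05, 28 per group. Normal approximation: n = 2 × (1.960 + 1.282)² × 5.6² / 5² = 26.4, so 27. The t-test gives 27.4, so 28. The figure reproduces and is unaffected by this point.

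**Is jaw a legitimate covariate?** Yes. The sites are chosen at visit 1 (Protocol 13.1.1), before implants are ordered and the distributor allocates treatment (Protocol 7.4). Jaw is therefore fixed before allocation.

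**How the noise arises.** Let D be the mean difference between jaws and s the SD, over randomisations, of the arm difference in mandibular share. Approximately,

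Var(without jaw term) = Var(with jaw term) + (D × s)².

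The extra error has mean zero, so it is imprecision and not bias. The documents give neither D nor s, so both rest on assumptions.

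**Set-up A (assumed).** 62 subjects; 60% (about 37) with at least one non-index implant; 35% of these implants mandibular and clustered within subjects; between-subject SD 4, within-subject SD 5. Simulated generalised least squares, 1,500 replicates per row. Variance cut = 1 − (SE with / SE without)²; added noise = √(SE without² − SE with²).

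| D (ISQ) | SE without | SE with | Variance cut | Added noise (ISQ) |
|---|---|---|---|---|
| 3 | 1.86 | 1.85 | 1% | 0.2 |
| 5 | 1.91 | 1.82 | 9% | 0.6 |
| 8 | 2.19 | 1.88 | 26% | 1.1 |
| 10 | 2.34 | 1.85 | 37% | 1.4 |

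A second run under the same assumptions gave 2, 11, 25 and 34%. Taken together: about 2, 10, 25 and 35%. At D = 0 the jaw term cost about 2% of variance.

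The low rows carry simulation error. The D = 8 and D = 10 rows imply s of about 0.14 (1.1/8 and 1.4/10), which would give 0.14 × 3 = 0.42 ISQ of added noise at D = 3, not 0.2. The figure at D = 3 is good only to a few percentage points.

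**Set-up B (different assumptions).** 31 subjects per arm, SD 5.6, 1–2 maxillary implants each, 30% or 50% of subjects with 1–3 mandibular implants, within-subject correlation 0.4. Random-intercept REML, 600 replicates. 95% CI half-widths for non-index implants:

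| D (ISQ) | 30%: without / with | 50%: without / with | Variance cut |
|---|---|---|---|
| 0 | 3.11 / 3.13 | 2.78 / 2.79 | −1% |
| 3 | 3.23 / 3.15 | 2.83 / 2.77 | 4–5% |
| 5 | 3.35 / 3.11 | 2.94 / 2.77 | 11–14% |
| 8 | 3.74 / 3.11 | 3.19 / 2.77 | 25–31% |
| 10 | 4.08 / 3.16 | 3.45 / 2.81 | 34–40% |

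Example at D = 5, 30%: 1 − (3.11/3.35)² = 14%. Across non-index and all-implant analyses, the CI without the jaw term was wider by about 2–3, 5–8, 13–20 and 19–29% at D = 3, 5, 8 and 10. Correlations of 0.2 and 0.6 gave 7–8% at D = 5 for non-index implants.

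The arm difference in mandibular share had an SD of 9–13 percentage points for non-index implants, so at D = 5 one SD of imbalance moves the estimate by 5 × 0.09 to 5 × 0.13 = 0.45 to 0.65 ISQ. For all implants the SD was 7–9 points, giving 0.35 to 0.45 ISQ.

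**Bone height.** No ISQ figure transfers directly; what matters is the jaw difference in SD units. D = 5 in set-up B is 5/5.6 = 0.89 SD, where the all-implant CI was about 5% wider (2.40 against 2.29 with 50% of subjects having mandibular implants).

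**What a jaw term does not do.** With an assumed coating effect of 5 in the maxilla and 0 in the mandible, the pooled estimate was about 3.6 (all implants) or 2.2 (non-index), with or without a jaw main effect.

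**The case against.** The case against is mostly about size. Randomisation makes the unadjusted comparison valid, its CI already reflects chance imbalance in jaw mix, and the primary endpoint is all-maxillary. All of that stands. A reader might infer that the secondary estimates are biased; they are not, averaged over randomisations.

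A reader might also take a wider CI as a fact. The documents do not support that. Protocol 18.3 speaks of bone quality and of where the coating effect will be larger; it gives no jaw difference in ISQ level, ISQ change or bone height. With no difference there is nothing to gain, and at 5 ISQ or less the CI is at most about 8% wider.

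Position is not ignored either. It is tabulated by arm, so an imbalance would be visible, and it is in the exploratory models, including those listed for 12-week ISQ and 24-month bone height (SAP 7.1). Protocol 18.2 also offers a conditional adjustment wider than the SAP's. Neither closes the gap: the exploratory models search for predictors and do not define the planned treatment estimate, and a significance trigger can miss an imbalance large enough to move it. SAP 6 does not list the narrowing of the rule as a change from protocol.

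Finally, bone quality may be the more direct covariate, and a jaw main effect assumes one common coating effect. Both are fair; neither argues for leaving jaw out.

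**Conclusion.** The omission is real: no passage puts jaw or position into the planned secondary comparison of coated and uncoated implants for multi-implant outcomes. The consequence is possible loss of precision in secondary analyses. It is not bias, and it does not touch the primary result.

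The size depends on the jaw difference, the mandibular share and the variance components, none of which the documents give. The two set-ups agree closely from 8 ISQ upwards and differ by a few percentage points at 3 and 5 ISQ. Change scores would gain less if the jaws differ less in change than in level. The point is worth acting on because the remedy is nearly free and is credible only if fixed before unblinding.

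**What to change.** In SAP 4.1, prespecify jaw (maxilla or mandible) as a fixed effect in every mixed model for non-index or all implants: ISQ level and change, and marginal bone height level and change. In the same edit, reconcile the conditional adjustment rule in SAP 4.1 with Protocol 18.2, or list the narrowing in SAP 6.

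The data are already collected. The cost is one degree of freedom and, if jaw is not prognostic, about 1–2% of variance. Because Protocol 18.3 expects a larger effect in the maxilla, a supportive treatment-by-jaw estimate could be added; the main effect alone does not answer that question.
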